#### **6.10.6 Subgroup Analyses**

The results for the primary and secondary endpoints will be further analyzed on the patients with a background AD-specific therapy, and those not on a background AD-specific therapy as well as for disease severity (patients who have a CDR score of 0.5 versus 1.0). Another subgroup analysis will be performed base on patient baseline body weight (<80 kg and ≥80kg).

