4.3. Removal of Subjects from Treatment

In accordance with the current revision of the Declaration of Helsinki and other applicable regulations, a subject has the right to withdraw from the study at any time and for any reason without prejudice to his or her future medical care by the physician or at the institution. A subject's participation may also be discontinued by the Investigator or Sponsor due to compliance, safety, or other administrative reason (see also [Section 6.2.12](#)).

The subject **must** be discontinued from the study for the occurrence of an unacceptable toxicity, including any of the following:

- ALT or AST $> 8 \times$ ULN; ALT or AST $> 5 \times$ ULN for > 2 weeks; or ALT or AST $> 3 \times$ ULN and total bilirubin $> 2 \times$ ULN or INR > 1.5 ; or ALT or AST $> 3 \times$ ULN with the appearance of worsening of fatigue, nausea, vomiting, right upper quadrant pain or tenderness, fever, rash, or eosinophilia.

Refer to [Section 3.1.4](#) for details regarding follow-up after early discontinuation. Additional care and treatment will be provided to subjects once study discontinuation, including any required follow-up visits for resolution for study-related AEs, is completed.

Subjects who withdraw from the study treatment and/or study for a reason prior to Day 21 will be replaced.

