### 4 SAMPLE SIZE

Up to 76 subjects per treatment arm (152 total) provides 90% power to detect ES of 0.53 and 80% power to detect ES of 0.46. This level of ES is the minimum treatment effect amount considered clinically relevant and is less than the effect size seen in the Phase 2a studies.

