### 5 RANDOMIZATION

Randomization was stratified by 1) background AD-specific therapy (cholinesterase inhibitor or memantine versus no cholinesterase inhibitor or memantine); and 2) CDR-Global Score of 0.5 versus 1.0.

Eligible subjects were randomized 1:1 to two treatment arms: Neflamapimod 40mg or placebo utilizing a central Interactive Web Response System (IWRS).

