## 6.10 Efficacy Analyses

All efficacy analyses will be based on the Evaluable Efficacy Population by randomized treatment regardless of the treatment actually received. Descriptive statistics by treatment group

and visit will be reported for all efficacy endpoints. All statistical tests will be performed using a two-tailed 5% overall significance level, unless otherwise stated. All comparisons between treatments will be reported with 95% confidence intervals for the difference.

There will be no imputation of missing efficacy data.

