14.2.5.3	Mixed Models for Repeated Measures Analysis of Combined Change from Baseline in Z-score of Total Recall and Delayed Recall on the Hopkins Verbal Learning Test – Revised (HVLTL-R) by Background AD-specific Therapy Efficacy Population	IP	
14.2.6.1.1	Wechsler Memory Scale (WMS) Subscore, Cholinesterase Inhibitor or Memantine Efficacy Population	IP	
14.2.6.1.2	Wechsler Memory Scale (WMS) Subscore, No Cholinesterase Inhibitor or Memantine Efficacy Population	IP	

14.2.6.2.1	Wechsler Memory Scale (WMS) Composite and Overall Score, Cholinesterase Inhibitor or Memantine Efficacy Population	IP	
14.2.6.2.2	Wechsler Memory Scale (WMS) Composite and Overall Score, No Cholinesterase Inhibitor or Memantine Efficacy Population	IP	
14.2.6.3	Mixed Models for Repeated Measures Analysis of Change from Baseline in Wechsler Memory Scale (WMS) Immediate and Delayed Recall Composite Score (0-228) by Background AD-specific Therapy Efficacy Population	IP	14.2.5.3
14.2.6.4.1	Clinical Dementia Rating (CDR), Cholinesterase Inhibitor or Memantine Efficacy Population	IP	
14.2.6.4.2	Clinical Dementia Rating (CDR), No Cholinesterase Inhibitor or Memantine Efficacy Population	IP	
14.2.6.5	Mixed Models for Repeated Measures Analysis of Change from Baseline in Clinical Dementia Rating Scale-Sum of Boxes (CDR-SB) by Background AD-specific Therapy Efficacy Population	IP	14.2.5.3
14.2.6.6.1	Mini-Mental State Examination (MMSE), Cholinesterase Inhibitor or Memantine Efficacy Population	IP	
14.2.6.6.2	Mini-Mental State Examination (MMSE), No Cholinesterase Inhibitor or Memantine Efficacy Population	IP	
14.2.6.7	Analysis of Covariance of Change from Baseline in Mini-Mental State Examination (MMSE) Score by Background AD-specific Therapy Efficacy Population	IP	
14.2.6.8.1	CSF Biomarkers (T-tau, P-tau181, A $\beta$ 1-40, A $\beta$ 1-42, Neurogranin, Neurofilament Light Chain, pTau/A $\beta$ 1-42 Ratio), Cholinesterase Inhibitor or Memantine Efficacy Population	IP	
14.2.6.8.1	CSF Biomarkers (T-tau, P-tau181, A $\beta$ 1-40, A $\beta$ 1-42, Neurogranin, Neurofilament Light Chain,	IP	

	pTau/A $\beta$ 1-42 Ratio), No Cholinesterase Inhibitor or Memantine Efficacy Population		
14.2.6.9.1	Analysis of Covariance of Change from Baseline in CSF Biomarker (T-tau) by Background AD-specific Therapy Efficacy Population	IP	14.2.6.7
14.2.6.9.2	Analysis of Covariance of Change from Baseline in CSF Biomarker (P-tau181) by Background AD-specific Therapy Efficacy Population	IP	14.2.6.7

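### SAP 6.10.6 specifies no treatment-by-subgroup interaction, so its planned output does not directly estimate whether the treatment effect differs between subgroup levels

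*SAP*

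**What the plan says.** SAP 6.10.6 sets out three subgroup factors for the primary and secondary endpoints. Patients are to be "further analyzed on the patients with a background AD-specific therapy, and those not on a background AD-specific therapy"; the same is planned for CDR 0.5 versus 1.0; and "Another subgroup analysis will be performed base on patient baseline body weight", cut at 80 kg. The first two factors are also the randomization strata (SAP 5). Weight is not.

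The primary MMRM in SAP 6.10.2 contains background therapy and CDR as main effects only, and its single interaction is visit by treatment. WMS and CDR-SB use the same model. MMSE and the CSF markers use an ANCOVA with main effects and baseline (SAP 6.10.4). SAP 6.10.5 names no interaction for its exploratory subgroups either.

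In the table list (SAP 11), descriptive tables are split by level and the models carry titles such as "by Background AD-specific Therapy Efficacy Population" (Table 14.2.5.3). No table reports an interaction.

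On testing, SAP 6.10 states: "All statistical tests will be performed using a two-tailed 5% overall significance level, unless otherwise stated". The same section asks for a 95% CI for every treatment comparison. SAP 6.3.1 marks p-values below 0.05, 0.01 and 0.001 with asterisks. SAP 6.10.7 labels supportive analyses as descriptive and applies no multiplicity control.

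**The concern.** The question behind a subgroup analysis is whether the treatment effect differs between levels. The quantity that answers it is the difference between the two effects, with its uncertainty. The plan produces a treatment comparison for each level and stops there. Nothing says how the two are to be compared.

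In each level the sample is a fraction of a trial sized for 80% to 90% power overall, so a real and common effect will often cross 0.05 in one level and miss it in the other by chance. A table with one starred and one unstarred level then looks like evidence that the drug works in one group only. What is at stake is the interpretation of these tables for the primary and secondary endpoints, not the primary test.

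**Working it through.** **Inputs**
- Two-sided alpha 0.05 (SAP 6.10).
- 76 subjects per arm (SAP 4). Allocation (SAP 5): "Eligible subjects were randomized 1:1 to two treatment arms".
- Design effects (SAP 4): the sample size "provides 90% power to detect ES of 0.53 and 80% power to detect ES of 0.46". These are standardised, so SD = 1.
- Subgroup split: not in the documents. Assumed 50/50, 60/40 and 70/30, with 1:1 allocation within each level, so n1 = 76f and n2 = 76(1 − f) per arm.
- Dropout: SAP 4 makes no allowance. Protocol 4.3 says only: "Subjects who withdraw from the study treatment and/or study for a reason prior to Day 21 will be replaced". Taken as 0%, with 10% and 20% as an assumed range.
- Week 24 is treated as a two-sample comparison on the standardised scale. Precision gained from MMRM covariates is not modelled.

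**Step 1: the plan's own figure**

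Power = Φ(d√(n/2) − 1.96) + Φ(−d√(n/2) − 1.96); the second term is negligible here.
- d = 0.53, n = 76: 0.53 × √38 = 3.267, power 90.4% (noncentral t: 90.1%).
- d = 0.46, n = 76: 0.46 × √38 = 2.836, power 80.9% (noncentral t: 80.4%).

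Both agree with SAP 4.

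**Step 2: a common effect, tested separately in two levels**

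The levels contain different patients, so the two tests are independent and P(exactly one significant) = p1(1 − p2) + p2(1 − p1).

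Example, ES 0.46 at 50/50 (38 per arm in each level): 0.46 × √19 = 2.005, so p1 = p2 = 51.8%, and 2 × 0.518 × 0.482 = 49.9%.

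| Common ES | Split | Power, larger level | Power, smaller level | Exactly one significant (normal) | Same (noncentral t) |
|---|---|---|---|---|---|
| 0.46 | 50/50 | 51.8% | 51.8% | 49.9% | 50.0% |
| 0.46 | 60/40 | 59.3% | 43.4% | 51.2% | 51.3% |
| 0.46 | 70/30 | 66.0% | 34.2% | 55.0% | 55.2% |
| 0.53 | 50/50 | 63.7% | 63.7% | 46.2% | 46.8% |
| 0.53 | 60/40 | 71.6% | 54.2% | 48.2% | 48.8% |
| 0.53 | 70/30 | 78.0% | 43.2% | 53.8% | 54.5% |

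The range is about 46% to 55% per factor. With 10% or 20% dropout it is 48% to 55%. At 80/20 it rises to 61% (ES 0.46) and 63% (ES 0.53).

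**Step 3: dependence on the true effect (50/50 split)**

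P(exactly one significant) is 9.5% at ES 0, 24% at 0.20, 38% at 0.30, 40% at 0.59, 25% to 26% at 0.69 and 7% to 8% at 0.86, where the pairs are the normal and noncentral t results. The last three effect sizes are the values tabulated for Phase 2a in Protocol 1.3.

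**Step 4: the interaction test**

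z = (d1 − d2) / √(2/n1 + 2/n2). With a common effect it rejects at its nominal level, and simulation gave 5.0% per factor.

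At 50/50 the standard error is √(2/38 + 2/38) = 0.324.
- Power for a true difference of 0.46 SD: Φ(0.46/0.324 − 1.96) = 29%.
- Power for a true difference of 0.53 SD: 37%.
- Difference needed for 80% power: (1.96 + 0.8416) × 0.324 = 0.91 SD (0.99 SD at 70/30).

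**The case against.** The strongest reply is that these analyses are labelled descriptive (SAP 6.10.7), carry a 95% CI for each comparison (SAP 6.10), and come with no instruction to compare p-values across levels. That stands. The 46% to 55% is the chance that exactly one level is significant, not the chance that anyone draws a wrong conclusion. It becomes misleading only when a reader contrasts the two levels. It does not remove the point, because the 5% tests and the asterisk convention invite that contrast and the plan offers no direct estimate to put in its place.

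Four stronger readings are tempting, and the documents do not support them.
- That a discordance of about one half is a fixed property of the plan. It depends on the true effect and on the split, and the documents give no subgroup sizes.
- That subgroup tables will select the Phase 3 population. Protocol 1.3 says only that the CDR will help estimate effects for Phase 3 design; it mentions neither subgroups nor a choice of population.
- That the difference cannot be recovered. The levels are disjoint, so if models are fitted separately the difference and its standard error, √(SE1² + SE2²), follow from the planned estimates and CIs. What is missing is the specification and the reported result.
- That models are certainly refitted within each level. A table titled by factor could mean separate fits or one joint model. SAP 6.10.6 does not say, though separate fits are the likelier reading.

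The number of unadjusted subgroup tests is a separate multiplicity matter that SAP 6.10.7 discloses and that interaction terms would not remove.

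**Conclusion.** The point holds as a cheap improvement to the subgroup analyses. The omission is consistent across the model text, the subgroup section and the table list. If the effect is common and of design size, and subgroup splits lie between 50/50 and 70/30, roughly half of trials would show one significant and one non-significant level for a given factor. A direct test of the difference would wrongly signal one in about one trial in twenty. The discordance is much smaller if the drug does nothing or if its effect is near the top of the Phase 2a range.

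The interaction test is weak at this sample size and would seldom settle whether levels differ. The gain is an honest estimate of the difference with its interval, not a decisive test. The primary test, its estimate and its error rate are unaffected.

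**What to change.** In SAP 6.10.6, specify for each factor one model on the whole Efficacy Population:
- **MMRM endpoints (HVLT-R z-score, WMS, CDR-SB):** add treatment-by-subgroup, subgroup-by-visit and treatment-by-subgroup-by-visit. Background therapy and CDR are already main effects; the weight analysis also needs a weight main effect.
- **ANCOVA endpoints (MMSE, CSF markers):** add treatment-by-subgroup, again with a weight main effect for the weight analysis.
- **Reporting:** give the difference in treatment effects (Week 24 for MMRM endpoints, the analysed time point for ANCOVA endpoints) with its 95% CI and interaction p-value, beside the within-level estimates and CIs from the same model. Add these to the table list in SAP 11.
- **Scale:** report the difference on the untransformed scale even if the rank-based analysis in SAP 6.10.2 is triggered, because ranking changes what an interaction means.
- **Interpretation:** state that within-level p-values will not be used to claim a differential effect, and that a non-significant interaction will not be read as evidence of a common effect. The estimate and CI should lead.

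The cost is a few extra model terms and some programming, with no new data, visits or patients. The limitation to state openly is low power: about 29% for a difference of 0.46 SD at a 50/50 split, with about 0.91 SD needed for 80%.

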#### **6.10.7 Multiplicity**

All secondary endpoints and the supportive analyses will be considered as descriptive evidence of efficacy and will be analyzed without any procedures to account for multiple comparisons.

### **6.11 Pharmacokinetic Analysis**

Neftamapimod concentration values will be reported for the PK population. All PK data collected will be included in data listings sorted by treatment, patient and time point, as appropriate.

Individual values and descriptive statistics for the plasma concentrations of neftamapimod will be summarized by neftamapimod treatment and by visit. Boxplots of the distributions of neftamapimod concentrations by visit will be used to present graphical summaries of neftamapimod concentration data.

Trough and maximum concentrations ( $C_{\text{Trough}}$  and  $C_{\text{max}}$ , respectively) will be obtained on Day 21 (i.e., at steady-state) for each subject by observation and descriptive statistics for the neftamapimod treatment group will be presented.

In addition, the effect of CYP2C19 genotype status on PK parameters will be investigated.

The robust PK parameters (i.e. PPK model derived  $C_{Trough}$  and  $C_{max}$ , AUC and etc.) will be derived by an integrated population pharmacokinetic (PPK) analysis. PPK analysis plan will be detailed in a separate Pharmacometrics Analysis Plan and reported separately from the study results.

## 6.12 Pharmacokinetic-Pharmacodynamic Analyses

Analyses of CSF biomarkers (T-tau, P-tau181, A $\beta$ 1-40, A $\beta$ 1-42, neurogranin, neurofilament light chain) will use observational Trough and maximum concentrations ( $C_{Trough}$  and  $C_{max}$ , respectively) on Day 21 as exposure parameters in the initial PK-PD analysis. For numerical PD endpoints, both absolute and percent change from pre-treatment assessments will be performed, as appropriate. Number and percent will be provided for categorical PD parameters (e.g. CYP2C19). Overall, summary statistics and for each treatment group for biomarkers will be presented and a by-subject listing of plasma biomarker results will be provided as an appendix.

Additional PK-PD exploratory analyses may be performed to further study the effects of the treatment via PK parameters (i.e.  $C_{Trough}$  and  $C_{max}$ ) on HVLt-R, WMS, CDR, and/or CSF biomarkers, as warranted by data. Nominal  $C_{Trough}$  and  $C_{max}$  will be summarized based on concentration values by nominal hour at Day 21 (i.e. 2.5 hour for  $C_{max}$  and 0 hour for  $C_{Trough}$ ).

For many endpoints, both absolute and percent change from pre-treatment assessments will be performed. All data collected and captured in the CRF will be included in data listings sorted by treatment, patient and time point, as appropriate.

## 6.13 Safety Analyses

The safety analyses will be presented by the treatment received for the Safety Population.

### 6.13.1 Adverse Events

A treatment emergent adverse event (TEAE) is defined as:

- Any AE with an onset on or after the first dose of study drug and through 30 days after the last dose of study drug in the double blind treatment period.
- Any pre-existing AE that has worsened in severity on or after the first dose of study drug and through 30 days after the last dose of study drug in the double blind treatment period.

A treatment-related AE is defined as an AE as being possibly related to the study drug. If an AE has a missing relationship, it is assumed to be related to the study drug for analysis purposes. Maximum severity will be assumed for an AE with missing severity.

The following tables will be presented for AEs:

- Overall incidence and the number of AEs, SAEs, Treatment related TEAEs, TEAEs leading to withdrawal of study/study drug
- TEAE by system organ class and preferred term, incidence and number of events
- Treatment related TEAE by system organ class and preferred term, incidence and number of events
- Serious TEAE by system organ class and preferred term, incidence and number of events
- TEAEs leading to withdrawal of study drug by system organ class and preferred term, incidence and number of events
- TEAE by system organ class, preferred term and maximum severity, incidence
- Listing of serious TEAEs (presented in the Table section of the appendices)
- Listing of deaths (presented in the Table section of the appendices)

Adverse events will be coded using MedDRA version 21.0.

A complete subject listing of all AEs will be provided. This listing will include treatment, AE verbatim term, primary system organ class and preferred term, the time of onset and cessation of event relative to the first dose of study drug, duration of AE (for ongoing AEs, no duration will be calculated), whether serious, severity, relationship to study drug, action taken and outcome.

In counting the number of AEs reported, a continuous event (i.e. reported more than once and which did not cease), will be counted only once; non-continuous AE reported several times by the same subject will be counted as multiple events.

### **6.13.2 Laboratory Data**

Descriptive statistics of the observed values and change from baseline (continuous data) will be presented by treatment group and visit for each hematology, serum chemistry, and coagulation parameter. Each measurement (continuous data) will be classed as below, within, or above normal range, based on ranges supplied by the laboratory used. Shift tables in relation to the normal range from baseline to each follow-up visit will be presented.

A listing of any clinically significant laboratory measurements recorded throughout the study will be presented.

### **Liver Function Parameter**

The number and percentage of subjects meeting certain liver function abnormality categories will be summarized by visit:

- Alanine Aminotransferase (ALT) assessment > 3 times upper limit of normal (ULN),

- Aspartate aminotransferase (AST) > 3xULN,
- ALT or AST: > 3xULN; > 10xULN; > 20xULN
- Total Bilirubin: > 1.5xULN; > 2xULN
- Alkaline Phosphatase: > 1.5xULN; >2xULN
- (ALT or AST > 3xULN) and total bilirubin>2xULN
- (ALT or AST>3xULN) and total bilirubin>2xULN and alkaline phosphatase<2xULN

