3.2.1.2. Safety Considerations

Based on the clinical experience to date at higher doses and the results from animal toxicology studies, the neflamapimod dose of 40 mg BID and lower is expected to be well tolerated and to have a low risk of drug toxicity.

In the Phase 2a studies (Study 303) of 6- or 12-weeks neflamapimod dosing in patients with mild AD, a total of 25 subjects were enrolled. With regard to safety, neflamapimod was well tolerated, with 24 of 25 subjects completing their scheduled dosing period (8 completed 6 weeks neflamapimod administration, and 16 completing 12 weeks neflamapimod administration). The one subject who discontinued early did so within the first week of study drug administration due to an adverse event (AE) of vomiting, attributed primarily to persistent CSF leakage after the predose/baseline CSF collection. There were no severe or serious AEs reported. The most common AEs across the 2 studies were mild somnolence (sleepiness or drowsiness) reported in 5 patients, and self-limited mild diarrhea (loose stools) reported in 4 patients. There was also one event of moderate diarrhea, which was considered not related, as the event did not recur during additional 8 weeks of treatment after having resolved during a brief treatment interruption. No treatment-related or clinically relevant trends in the analysis of safety laboratory and 12-lead electrocardiogram (ECG) parameters were observed. More specifically, there were no abnormalities in liver function tests (LFTs), nor any trends in changes in LFT parameters, noted in either study. LFT abnormalities, specifically increases in liver transaminases, were seen in 10% to 15% of patients in a prior study in patients with RA at a dose of 250 mg BID for 3 months. Due to the use of different formulations in the RA studies, the plasma drug concentrations were 4- to 5-fold higher than in the Phase 2a mild AD studies.

The 40 mg BID dose level provides a 5-fold margin based on plasma drug levels to no adverse effect level and 10-fold margin to minimal and/or equivocal findings for hematological, hepatic and

neuropathological changes in chronic (9- and 12-month) dog toxicology studies. Further details are provided in the investigator brochure.

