### **6.2.17 Unscheduled Visits**

In general, only scheduled post-baseline laboratory, ECG, and vital signs values will be tabulated. Post-baseline repeat/unscheduled assessments will be disregarded from table, although these post-baseline assessments will be listed in the relevant appendices to the CSR.

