### 6.13.4 Electrocardiogram Data

Descriptive statistics for observed values and changes from baseline in the following 12-lead ECG variables will be tabulated at each follow-up visit:

- Heart rate (beats/min)
- PR interval (msec)
- RR interval (msec)
- QRS complex (msec)
- QT interval (msec)
- QTc interval (msec)
- QTcF interval (msec) [Fridericia's formula - QTcF]

ECG Result Interpretation (Normal, Abnormal Not Clinically Significant [NCS], and Abnormal Clinically Significant [CS]) will be summarized by treatment group and visit.

The incidence of ECG abnormalities for subjects with any abnormal CS ECG result will be presented by treatment group and visit.

Additionally, the number and percentage of subjects in each treatment group who meet any of the following criteria for QT or QTcF will be tabulated by treatment group and visit.

- Maximum value >450 to 480 msec
- Maximum value >480 to 500 msec
- Maximum value >500 msec
- Maximum increase from baseline >30 to 60 msec
- Maximum increase from baseline >60 msec

Shift tables in relation to the overall interpretation (Normal, Abnormal NCS, and Abnormal CS) from baseline to each follow-up visit will be presented.

Box plots for ECG data will be provided for changes from baseline by visit and maximal change.

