14.2.6.17.3	Analysis of Covariance of Change from Baseline in Mini-Mental State Examination (MMSE) Score by Disease Severity Efficacy Population	IP	
14.3	Safety Data		
14.3.1	Displays of Adverse Events		
14.3.1.1	Adverse Events, Overview of Treatment-Emergent Adverse Events (TEAE) Safety Population	IP	
14.3.1.2	Adverse Events, TEAEs by Primary System Organ Class and Preferred Term Safety Population	IP	
14.3.1.3	Adverse Events, TEAEs by Preferred Term Safety Population	IP	
14.3.1.4	Adverse Events, Treatment-Related TEAEs by Primary System Organ Class and Preferred Term Safety Population	IP	
14.3.1.4.1	Adverse Events, TEAEs by Primary System Organ Clas, Preferred Term and Causality Safety Population	IP	14.2.4.1
14.3.1.5	Adverse Events, TEAEs Leading to Discontinuation of Study by Primary System Organ Class and Preferred Term Safety Population	IP	14.2.4.1
14.3.1.6	Adverse Events, Serious TEAEs by Primary System Organ Class and Preferred Term Safety Population	IP	14.2.4.1

14.3.1.7	Adverse Events, Treatment-Related Serious TEAEs by Primary System Organ Class and Preferred Term Safety Population	IP	
14.3.1.8	Adverse Events, TEAEs by Primary System Organ Class, Preferred Term and Maximum Severity Safety Population	IP	
14.3.1.9	Adverse Events, TEAEs [ $\geq 2\%$ ] by Primary System Organ Class and Preferred Term Safety Population	IP	
14.3.2	Listings Of Deaths, Other Serious And Significant Adverse Events		
14.3.2.1	Death, Listing Safety Population	IP	
14.3.2.2	Serious TEAEs, Listing Safety Population	IP	14.3.2.1
14.3.2.3	Treatment-Related TEAEs, Listing Safety Population	IP	14.3.2.1
14.3.2.4	TEAEs Leading to Discontinuation of Study, Listing Safety Population	IP	14.3.2.1
14.3.3	Narratives of Deaths, Other Serious and Certain Other Significant Adverse Events ( This is usually not created by stats but this placeholder )		
14.3.4	Abnormal Laboratory Values		
14.3.4.1	Hematology Safety Population	IP	
14.3.4.2	Shift Table - Hematology Safety Population	IP	
14.3.4.3	Chemistry Safety Population	IP	
14.3.4.4	Shift Table – Chemistry Safety Population	IP	14.3.4.2
14.3.4.5	Coagulation Safety Population	IP	
14.3.4.6	Shift Table – Coagulation Safety Population	IP	14.3.4.2
14.3.4.7	Liver Function Parameter and Coagulation Parameter Abnormalities Safety Population	IP	
14.3.5	Extent Of Exposure, Dosage Information, And Compliance		

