16.2.8.1.1	Hematology Results (Enrolled Subjects)	IP	

Listing Number	Listing Title	Validation Method	Shell Number (if repeat)
16.2.8.1.2	Chemistry Results (Enrolled Subjects)	IP	
16.2.8.1.3	Coagulation Results (Enrolled Subjects)	IP	
16.2.8.1.4	Clinically Significant Laboratory Results (Enrolled Subjects)	IP	
16.2.8.1.5	Laboratory Liver Function and Coagulation Parameter Abnormalities (Enrolled Subjects)	IP	
16.2.8.2	Vital Signs (Enrolled Subjects)	IP	
16.2.8.3	12-lead ECG Parameters (Enrolled Subjects)	IP	
16.2.8.4	Physical Examination, Abnormal Results (Enrolled Subjects)	IP	
16.2.8.5	Columbia Suicide Severity Rating Scale (C-SSRS) Questionnaire (Enrolled Subjects)	IP	

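### Liver threshold categories are summarized only by visit and without unscheduled or repeat samples, so no planned table gives the number of subjects per arm who ever crossed a threshold

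*SAP*

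**What the plan says.** SAP 6.13.2, under Liver Function Parameter, sets the unit of tabulation: "The number and percentage of subjects meeting certain liver function abnormality categories will be summarized by visit". The list beneath it holds single-analyte limits and two combined categories. One combined category reads "ALT or AST > 3xULN) and total bilirubin>2xULN"; the other adds an alkaline phosphatase condition. No any-time, worst-value or maximum count is named, and no time window is given for the combined categories. The INR limit follows under its own subheading with no tabulation rule.

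The other laboratory outputs in SAP 6.13.2 are descriptive statistics by visit, a listing of clinically significant values, and shifts: "Shift tables in relation to the normal range from baseline to each follow-up visit will be presented". SAP 6.2.17 adds: "Post-baseline repeat/unscheduled assessments will be disregarded from table".

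The SAP section 11 list has one liver threshold table, 14.3.4.7 ("Liver Function Parameter and Coagulation Parameter Abnormalities Safety Population"), and one matching subject listing, 16.2.8.1.5 ("Laboratory Liver Function and Coagulation Parameter Abnormalities (Enrolled Subjects").

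Elsewhere the SAP does use extremes. The QT categories in 6.13.4 are worded on a maximum (for example "Maximum value >450 to 480 msec"), ECG and vital signs have plots of maximal change, and adverse events have a table by maximum severity.

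**The concern.** A safety reader first wants to know how many subjects in each arm ever exceeded three times the upper limit of normal. A by-visit table does not answer this. A subject raised at three visits adds to three rows, while three subjects raised once each produce the same rows.

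The combined ALT/AST-plus-bilirubin category has a second problem. If both limits must be exceeded within one visit row, rises that peak at different visits count as zero throughout.

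The rule on unscheduled samples makes both problems worse. Protocol 4.3 includes a criterion on an enzyme rise lasting more than two weeks, and scheduled chemistry is six weeks apart between Days 42 and 126. Confirming that criterion would normally need an extra sample, and that sample enters no table.

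Liver enzymes deserve a clear display here. Protocol 3.2.1.2 reports from earlier use of the drug: "LFT abnormalities, specifically increases in liver transaminases, were seen in 10% to 15% of patients in a prior study". SAP section 8 plans no data safety monitoring board analysis, so the end-of-study tables carry the comparison between arms.

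**Working it through.** **Design figure.** The plan gives no liver figure to reproduce. Its only design figure is 76 per arm (SAP section 4). With power = Φ(ES × √(n/2) − 1.96) and n = 76, √38 = 6.164:

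- ES 0.53: 0.53 × 6.164 = 3.267; Φ(1.307) = 0.904, against 90% stated.
- ES 0.46: 0.46 × 6.164 = 2.836; Φ(0.876) = 0.809, against 80% stated.

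Both reproduce. The liver point does not depend on them; 76 serves only as the denominator.

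**Number of rows.** As Protocol Table 6-1 reads, post-baseline chemistry falls on Days 21, 42, 84 and 126 and at Follow-up, so K = 5, plus Early Termination for those who stop early. The printed table may have lost marks, so K = 5 is an assumption. As read, no chemistry is marked at Day 168. Follow-up is then at about 168 + 14 = Day 182, which is 56 days after Day 126.

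**Bounds on the ever-crossed count.** Let c_k be the count in row k and E the number of subjects who ever crossed. Then

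max(c_k) ≤ E ≤ min(76, Σ c_k).

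With c_k = 2 in each of five rows, E lies between 2 (2/76 = 2.6%) and 10 (10/76 = 13.2%). The same printed table fits both. The bounds cover scheduled samples only. Under SAP 6.2.17, a crossing seen solely on a repeat sample adds to E and to no row.

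**Dilution across rows (background only).** Suppose 10% to 15% of an arm ever crossed: 7.6 to 11.4 subjects.

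- Each raised at one visit: 7.6/5 = 1.5 to 11.4/5 = 2.3 subjects per row, or 2% to 3%.
- Each raised at two visits: 3.0 to 4.6 per row.

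**Combined category.** Take ALT at 4 times the limit on Day 84, then ALT at 2.8 times with bilirubin at 2.2 times on Day 126. The Day 84 row fails on bilirubin and the Day 126 row fails on ALT. The subject counts 0 in every by-visit combined row and 1 in a table built on peak values.

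**The case against.** The strongest reply is that the cases that matter most appear elsewhere.

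- Protocol 4.3 requires discontinuation at stated enzyme limits, including ALT/AST with bilirubin. Protocol 7.1.4 makes a new or worsened abnormality that leads to discontinuation an adverse event. SAP 6.13.1 tabulates such events, and those leading to withdrawal, by subject over the whole treatment period. Listing 16.2.8.1.5 keeps the subject-level values. A reader might infer that a true liver signal would go unseen; given these outputs, the documents do not support that. What remains uncovered is incidence at a fixed threshold: an asymptomatic rise above three times the limit need not become an adverse event, and a listing is not a count by arm.
- The shell of Table 14.3.4.7 is not in the documents and its title does not say by visit. SAP section 6 permits extra tables, and SAP 6.2.17 is worded as a general rule. An any-time row could therefore still appear. None is planned in the text.
- Same-visit concurrence is inferred from the by-visit lead-in and not stated. Nor do the documents say how Early Termination chemistry is tabulated: SAP 6.2.16 assigns those visits for efficacy data only. A separate Early Termination row is thus a possible reading and not a stated rule.
- It is tempting to size the loss with p-values. With 76 per arm, 8 versus 1 in an any-time row gives a two-sided Fisher p of 0.034, while 2 versus 0 in a single visit row gives 0.50. The documents do not support leaning on this. No liver test is planned. The 10% to 15% figure has no stated threshold and came at 250 mg BID with plasma levels 4- to 5-fold higher, and Protocol 3.2.1.2 reports no liver test abnormalities in the two Alzheimer's studies. The result is also fragile: 8 versus 2 gives 0.098, 8 versus 3 gives 0.21, and 4 versus 1 gives 0.37.
- For INR the fragmentation argument is weak, since Table 6-1 as read has only Day 84 and Follow-up after baseline.

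**Conclusion.** The point holds as a reporting gap. As SAP 6.13.2 and 6.2.17 stand, no planned table yields the number of subjects per arm who ever exceeded a liver threshold. In the five-row illustration the uncertainty is 2 to 10 of 76. The bounding argument needs no assumption about event rates; the illustration assumes five scheduled post-baseline chemistry visits. The zero count for non-coinciding ALT/AST and bilirubin rises rests on the natural by-visit reading, and the missing definition is itself worth settling. The earlier-study rate is background and carries no weight in this conclusion.

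No collected data are lost, and efficacy, power, alpha and monitoring during the trial are untouched. The change is still worth making before database lock because it is cheap and gives the liver displays the worst-value view the SAP already uses for adverse event severity, QT categories and plots of maximal change.

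**What to change.** 1. In SAP 6.13.2 and Table 14.3.4.7, add an any-post-baseline row per arm for every liver category and for INR. Count each Safety Population subject once by the worst value, and include Early Termination, Follow-up, unscheduled and repeat samples.
2. Add a matching exception to SAP 6.2.17. Without it, the new row would still omit peaks seen only on a repeat sample.
3. Report the combined ALT/AST-plus-bilirubin category in two ways: concurrent (same sample date or a window stated in advance) and any-time peak values. Peaks alone could pair a Day 21 ALT with a Follow-up bilirubin about 182 − 21 = 161 days later.
4. State which alkaline phosphatase value applies in the category that uses it, for example the one from the same sample as a named qualifying value.
5. Keep the by-visit rows as detail. A between-arm difference with a 95% confidence interval is optional.

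The cost is SAP wording and one extra table block from data already collected. The any-time combined row may bring in a few non-concurrent cases that need narrative review.
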